CD Cluster Differentiation

CFR Code of Federal Regulations

EDC Electronic Data Capture

G-CSF Granulocyte Colony Stimulating Factor

HIPAA Health Insurance Portability and Accountability Act

HIT High-Intensity Training

HPC Hematopoietic Progenitor Cells

HSD Tukey's Honestly Significant Difference

HSC Hematopoietic Stem Cells

ICF Informed Consent Form

IRB Institutional Review Board

mL Milliliters

MSC Mesenchymal Stem Cells

NIRS Near-infrared Spectroscopy

NSAIDS Non-steroidal anti-inflammatory drugs

PI Primary Investigator

SAE Serious Adverse Event

SAS Statistical Analysis System

Version 2.0

Version Date: 01NOV2022

Quantification of Peripheral Hematopoietic Progenitor Cell Circulation Following Repeated
Acute, Vascular Restriction Resistance Exercise Using the Delfi Tourniquet System

UP Unanticipated Problem

1-RM One-repetition Maximum

Quantification of Peripheral Hematopoietic Progenitor Cell Circulation Following Repeated Acute, Vascular Restriction Resistance Exercise Using the Delfi Tourniquet System

1 Scientific Rationale / Background

Intense interest in the areas of orthopedic surgery and recovery science has been placed on progenitor cell research. The ability to transplant these cells in successful patient engraftments has been sought after due to properties of hematopoietic stem cells (HSCs) that allow for long-term self-renewal and multipotency (1). The obstacle of an immunocompetent immune system has been a source of difficulty for some time within the scientific community (2). Using stem cells from different regions of the same patient prevents the need for long-term immune system suppression (2, 3). Currently, HSCs are collected through two primary methods: bone marrow aspiration and peripheral harvest following pharmaceutically induced mobilization using granulocyte colony-stimulating factor (G-CSF). These methods suffice but less invasive methods are preferred. By quantifying peripheral hematopoietic progenitor cell presence within the blood following repeated blood flow restriction exercise, we hope to uncover a more convenient method for harvesting these hematopoietic progenitor cells. We aim to accomplish this with the aid of exercise-induced elevation of progenitor cell concentration in peripheral blood (4, 5). Prior studies with BFR and stem cell mobilization have shown increased cell concentration immediately post a single bout of exercise (6).

Also present within peripheral blood following exercise are adult mesenchymal stem cells (MSCs). MSCs can monitor their local and systemic environments for pertinent stimuli. These stimuli such as often determine the fate and commitment of MSC differentiation (7). MSCs utilize paracrine effects to conduct this interaction with their surrounding (8). MSCs can also respond to changes in environmental conditions and hypoxia, as seen in animal studies (9), as well as exercise, seen in human studies (4). MSCs have the same primary methods of collection as HSCs.

Blood Flow Restriction Therapy (BFR) has been successfully implemented during the post-operative rehabilitation period, for patients with osteoarthritis or muscle atrophy, and in instances of limb salvage following injury (10-13). This type of training has been shown to also be effective in producing hypertrophic skeletal muscle growth that can parallel growth seen in High-Intensity Training (HIT), but without the mechanical muscle damage that occurs with HIT (13-18). Blood flow restriction training is an alternative method to traditional exercise for the goal of retaining and increasing muscle mass without the musculoskeletal stress placed on the body by traditional training methodologies. The application of BFR uses low-intensity resistance training with high repetition volume to mimic the exertion required of the body by higher-intensity, lower-repetition training (19).

The mechanism by which BFR training acts is not fully understood. Some of the leading theories for the mechanism are the metabolite theory, which includes, increased cellular swelling through the accumulation of metabolites and blood within the muscle cells, increased protein synthesis and growth hormone production, elevated metabolic stress,

Quantification of Peripheral Hematopoietic Progenitor Cell Circulation Following Repeated Acute, Vascular Restriction Resistance Exercise Using the Delfi Tourniquet System

and heightened motor unit recruitment (20, 21). The influx of blood carrying metabolites during BFR to the area of injury facilitates elevation of growth hormone levels locally (21, 22). Local accumulation of metabolites has been indicated to influence the production of growth hormone more so than total metabolite production. (23, 24). These growth hormones can exhibit an anabolic effect on muscle. Increased metabolic stress results in the local accumulation of lactate, hydrogen ions among other metabolic byproducts (25, 26). Analysis of BFR from a physiological perspective have been consistent in determining that levels of lactate and growth hormone increase following BFR training, ultimately peaking in a time window immediately to 40 minutes after BFR (23, 27-29). Exercise using BFR has also been linked to extremely low oxygenation saturation (StO₂) levels within the skeletal muscle (<10%) as measured via near-infrared spectroscopy (NIRS). This finding suggests that the working tissue experiences severe hypoxia during BFR exercise (30). There have been inconsistent findings on if exercise within this hypoxic state is better suited to stimulate greater gains in muscle strength and physiologic structure change (31, 32). Further investigation on muscular and physiologic response to hypoxic training conditions could provide insight into a new way of conditioning the body without needing excessive load, a more ideal approach for the therapeutic patient recovery process. The final theory behind the action mechanism of BFR is motor unit recruitment. Motor unit recruitment using Henneman's size principle theorizes that motor unit recruitment within a motor pool begins with the smallest motor unit(s) and progresses to larger and larger motor units depending on the targeted force. Recruiting progressively higher threshold motor units is influential in generating muscle hypertrophy as external load determines motor unit recruitment (21). This idea paired with accompanying adjustments in repetitions has been at the core of much of the traditional approaches to hypertrophy development within musculature. Thus, the aim of this study is to quantify the cellular content (*in vitro*) of mobilized hematopoietic stem cells extracted from peripheral blood before exercise and at 0-, and 20-minute intervals following exercise. This study will be useful in the continued advancement of localized, peripheral hematopoietic progenitor cell research and patient application, development of effective non-surgical or post-surgical therapeutic treatments, and incorporation of knowledge in the implementation of performance training.

2 Study Design

The proposed study is a prospective, quasi-experiment, dual-center (laboratory and exercise facility) study involving 10 healthy male and 10 healthy female volunteers. A potential subject must clear the screening, consent to the procedures of this study, and complete the medical interview before proceeding with the familiarization session. The familiarization process will include an introduction to the Delfi BFR Tourniquet System (Delfi Medical Innovations Inc., Vancouver, BC) and the exercises (seated leg extension,

Quantification of Peripheral Hematopoietic Progenitor Cell Circulation Following Repeated Acute, Vascular Restriction Resistance Exercise Using the Delfi Tourniquet System

semi-reclined leg press, prone hamstring curl) that the subject will complete. The weight each subject will use for each exercise will be determined during this time. All familiarization procedures must be completed prior to the scheduling and execution of the first of twelve experimental testing sessions.

The experimental testing sessions will occur twice a week for six weeks (12 sessions) and will involve the BFR training utilizing the Delfi BFR Tourniquet System, as further described in the Experimental Testing Session section of the treatment plan (6.2). At the beginning of the first, the sixth, and the twelfth testing sessions there will be a blood draw requiring 6 cc of blood to be taken prior to exercise. Post-exercise, at each testing session, additional 6cc blood draws will be conducted immediately post exercise (time point 0), and 20 minutes after the conclusion of the workout. Following every testing session workout, finger-prick blood samples for lactate testing will be taken. These blood samples are to be taken at Time point 0- (T 0), 10-, and 20-minutes following exercise. Once the twelfth experimental testing session has been completed, the subjects will have one final session that is to take place no more than five days following the twelfth testing session. This final session will include one final blood draw of 6 cc. Throughout the duration of the study, the blood drawn will be used for obtaining a complete blood count (CBC) and for cellular analysis to quantify peripheral hematopoietic progenitor cell concentration. The blood samples collected from subject's fingers throughout the study will be used for analysis using a portable lactate analyzer. Lactate analysis will allow researchers insight into each subject's exertion level reflected by the amount of lactate found within the samples collected.

3 Objectives

3.1 Primary Objective

The primary objective of this study is to quantify the cellular content (*in vitro*) of mobilized hematopoietic stem cells and CBC data extracted from peripheral blood before exercise and at 0-, and 20-minute intervals following exercise.

3.2 Secondary Objectives

Post-exercise lactate levels and demographic information will be recorded to provide insight into the fitness development and endurance shift of each subject. Each peripheral blood sample will also be analyzed for MSC concentration if enough sample is available after primary testing.

3.3 Primary Effectiveness Endpoint

The primary effectiveness endpoint will be the quantification of mobilized hematopoietic stem cells and CBC data extracted from peripheral blood before exercise and at 0- and 20-minute intervals following exercise.

Quantification of Peripheral Hematopoietic Progenitor Cell Circulation Following Repeated Acute, Vascular Restriction Resistance Exercise Using the Delfi Tourniquet System

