3.4 Secondary Effectiveness Endpoints

Secondary effectiveness endpoints include post-exercise lactate levels, participant demographics, and MSC marker concentrations.

4 Hypotheses

4.1 Null Hypothesis:

H_0 - Subjects will have equal levels of hematopoietic progenitor cells (HPCs) before and after undergoing twelve experimental testing sessions with the Delfi BFR tourniquet system.

4.2 Alternative Hypothesis:

H_1 - Subjects will not have equal levels of hematopoietic progenitor cells (HPCs) before and after undergoing twelve experimental testing sessions with the Delfi BFR tourniquet system.

5 Participant Recruitment and Screening

The research study team intends to enroll a total of 25 volunteers (with 5 expected screen fails or withdraws)

Subject recruitment will occur through the Andrews Institute physician practices and physical therapy departments via word of mouth. Recruitment of subjects will also utilize a flyer displaying the opportunity for subjects to enroll in this study. Flyers will be placed in easily viewed spaces around the Andrews Institute campus in Gulf Breeze, FL. Potential study subjects will undergo a prescreening process covering inclusion and exclusion criteria through standard of care medical evaluations. Potential subjects meeting all inclusion criteria will have the study described to them by a member of the investigating team. This description will include potential risks, discomforts, and benefits. Subjects will then be provided an opportunity to read and sign an approved informed consent form. The subject will be provided sufficient time to consent and sign the informed consent form (ICF). The principal investigator (PI) will be available to answer any questions or provide clarifications during the informed consent process. This process will be completed before conducting any study related activities.

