used. Outcome measures will be those from pre and post exercise blood samples collected according to the study procedures (Section 5).

Outcome measures will be as follows:

Complete Blood Counts with differential: Red Blood Cell Count, White Blood Cell Count with differential, Total Nucleated Cell Count (number of nucleated cells per milliliter (mL)), Mononuclear Cell Count (number of mononuclear cells per mL), and Platelet Count (number of platelets per mL).

Flow Cytometry: Counts including cluster differentiation (CD) markers for HPCs and MSCs (if available).

Lactate Pro 2 Portable Lactate Analyzer (COSMED USA Inc., Concord, CA) Blood lactate level.

10 Statistical Considerations

Descriptive statistics will be compiled for all numeral measures. Analysis will be performed with a repeated-measures ANOVA and post-hoc Tukey's Honestly Significant Difference (HSD) for each numerical outcome variable. Significance will be set a priori at $p < 0.05$. With an alpha level of 5%, a beta of 10%, and an effect size of 200%, we calculated that a sample size of 10 is sufficient. Sufficient power has been confirmed on previous mobilization studies. The sample size of this study has been increased to 25 to account for potential subject withdrawal.

11 Quality Control and Assurance

All protocols will be monitored and analyzed data will be checked for accuracy by the principal investigator and/or a designated AREF study team member. All medical data will be kept in compliance with HIPAA guidelines.

Quantification of Peripheral Hematopoietic Progenitor Cell Circulation Following Repeated Acute, Vascular Restriction Resistance Exercise Using the Delfi Tourniquet System

12 References

2. Zakrzewski JL, van den Brink MR, Hubbell JA. Overcoming immunological barriers in regenerative medicine. *Nat Biotechnol*. 2014;32(8):786-94.
3. Caplan AI. Mesenchymal stem cells. *J Orthop Res*. 1991;9(5):641-50.

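### Sections 3.1 and 3.3 make progenitor-cell counts and all CBC data jointly primary, each tested at 0.05, while the only stated hypothesis (Section 4) concerns progenitor cells, so what counts as the primary result is unsettled

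*Protocol*

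**What the plan says.** - **Primary objective (Section 3.1):** to "quantify the cellular content (*in vitro*) of mobilized hematopoietic stem cells and CBC data extracted from peripheral blood", before exercise and at 0 and 20 minutes after it.
- **Primary endpoint (Section 3.3):** the "quantification of mobilized hematopoietic stem cells and CBC data", before exercise and at the same two times afterwards. No single variable is singled out, and no rule says which variable or variables must change.
- **Secondary endpoints (Section 3.4):** lactate, demographics and mesenchymal stem cell markers. CBC data are not among them, so the protocol places CBC in the primary tier only.
- **Hypotheses (Sections 4.1 and 4.2):** one pair. The null is "Subjects will have equal levels of hematopoietic progenitor cells (HPCs) before and after undergoing twelve experimental testing sessions"; the alternative is "Subjects will not have equal levels of hematopoietic progenitor cells (HPCs) before and after undergoing twelve experimental testing sessions". CBC does not appear.
- **Outcome list (Section 9):** "Complete Blood Counts with differential: Red Blood Cell Count, White Blood Cell Count with differential, Total Nucleated Cell Count", then "Mononuclear Cell Count (number of mononuclear cells per mL), and Platelet Count (number of platelets per mL"). Flow cytometry adds CD-marker counts for HPC, with the number of markers not stated.
- **Analysis (Section 10):** repeated-measures ANOVA with post-hoc Tukey HSD for each numerical outcome variable. "Significance will be set a priori at" p<0.05. No ordering of, or adjustment across, outcomes is given.

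**The concern.** The sections that define the primary endpoint and the section that states the hypothesis do not name the same thing. Section 3 puts a whole panel of counts into the primary tier; Section 4 puts one cell type there. Section 10 then gives every variable its own 5%. Tukey HSD controls error over the comparisons between draws within one variable. It does nothing across variables.

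Two things are at stake. First, if CBC variables are read as primary, the study has several chances of a chance finding that can be called primary. Second, and without any all-null assumption, a blood count may truly change after exercise while HPC does not. The endpoint as worded could then be reported as met although the Section 4 hypothesis was not supported. Section 1 gives the purpose as a more convenient way to harvest progenitor cells, which a CBC change alone would not support.

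**Working it through.** **The plan's own figure.** The protocol gives no error rate across outcomes. Its only related figure is the sample size of 10 in Section 10 (alpha 5%, beta 10%, effect size 200%). Reading 200% as a standardized difference of 2, a one-sided two-group normal formula gives 2 × (1.645 + 1.282)² / 2² = 4.3, so 5 per group and 10 in total. That is a calculation for one test. It says nothing about several primary variables and does not affect what follows.

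**Counting the primary variables.**
- Named in Section 9: red cells, white cells, total nucleated cells, mononuclear cells, platelets = 5.
- HPC, counted as one measure: 5 + 1 = 6.
- The white-cell differential is primary as well, but its number of parts is not stated. Assuming five parts: 6 + 5 = 11.

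**Assumptions for the error rate.** (a) Any one significant primary variable counts as a primary result. (b) No variable truly changes. (c) One two-sided test per variable at 0.05. The protocol gives no correlations between outcomes, so a range is shown.

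**Independent variables.** Chance of at least one false positive = 1 − 0.95^k.
- k = 6: 1 − 0.95^6 = 0.265
- k = 11: 1 − 0.95^11 = 0.431

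**Equal pairwise correlation r (simulated two-sided tests).**

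| r | 6 variables | 11 variables |
|---|---|---|
| 0.3 | 24.1% | 37.5% |
| 0.5 | 20.7% | 30.4% |
| 0.7 | 16.4% | 22.2% |
| 0.8 | 13.8% | 18.0% |
| 0.9 | 10.8% | 13.1% |

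Simulating repeated-measures ANOVA F-tests instead (20 subjects, 3 or 10 time points) gives nearly the same: for 6 variables about 27% at r = 0 and 17 to 18% at r = 0.7; for 11 variables about 43% and 23%.

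**Structural overlap.** The listed counts cannot be independent. Differential parts sum to the white-cell count, mononuclear cells are a subset of it, and total nucleated cells in circulating blood largely duplicate it. Model: total nucleated = white cells, mononuclear = two of five parts, everything else independent, 20 subjects, paired t-tests.
- 6 variables: about 22%. As a check, dropping the duplicate leaves five tests, and 1 − 0.95^5 = 0.226; the link between mononuclear and white cells lowers this slightly.
- 11 variables: about 35 to 36%.

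**If only Section 4 is confirmatory.** One HPC measure, one test: 5%.

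**Is naming HPC enough?** Section 4 compares before with after twelve sessions, a training effect. Section 3.3 compares pre-exercise with 0 and 20 minutes afterwards, an acute effect. Section 6.2 schedules those three draws at sessions 1, 6 and 12, giving 3 × 2 = 6 acute differences, and Section 6.3 adds a final resting draw. These are different contrasts. Naming HPC without naming the contrast does not yield one 5% test.

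**The case against.** The strongest reply is that the protocol never says any one significant CBC variable makes the study positive. Sections 3.1 and 3.3 are worded descriptively, as quantification, and the only inferential statement is the HPC hypothesis. On that reading the error rate is 5% and the CBC tests are supporting detail. A formal HPC hypothesis, an alpha and a beta do not by themselves make the CBC counts confirmatory. This stands as a limit on size: every figure above 5% is conditional. It does not remove the conflict, because Section 3.3 calls CBC data primary and nothing in the protocol confines confirmation to Section 4.

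A reader might infer that the primary endpoint simply has a 17 to 43% false-positive rate. The documents do not support that. The 43% needs 11 independent variables, but the number of differential parts is assumed and the overlap among the counts rules out independence. Nor is 17% a floor, since six variables at r of 0.8 to 0.9 give 11 to 14%. All figures also need nothing to change at all, whereas Section 1 cites earlier work showing raised cell concentration after one bout.

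A further reply is that adjustment across outcomes may sit in an analysis plan not shown. That is fair, and its absence alone is not the point. The point rests on text that is present: two definitions of what is primary, and a stated 0.05 for each outcome.

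Finally, this is an uncontrolled study in healthy volunteers, so the practical consequence is limited. That bears on weight, not on whether the sections agree.

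**Conclusion.** The point holds as an internal conflict. Sections 3.1 and 3.3 make HPC and CBC data jointly primary, Section 4 tests HPC only, and Section 10 gives each outcome its own 0.05. A CBC change alone could be reported as the primary result.

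The error rate is 5% if only Section 4 is confirmatory with one measure and one test. If any one variable counts and nothing truly changes, it is above 5% throughout the range examined: from about 11% (six variables, r = 0.9) through 22% (six, with overlap) to 35 to 36% (eleven, with overlap, on the assumed five-part differential). The independent-variable figures of 26% and 43% are reference values, not estimates. Several HPC markers, or several F-tests per outcome, would add to these.

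**What to change.** 1. In Sections 3.1 and 3.3, name one HPC measure (which flow-cytometry marker definition, in which unit) as the single primary variable.
2. Name one primary contrast, by reconciling Section 4 (before versus after twelve sessions) with Section 3.3 (pre-exercise versus 0 and 20 minutes post-exercise). State which draws form it, use the same words in Sections 3.3, 4 and 10, and list the other comparison as secondary.
3. Move the CBC variables to Section 3.4. In Section 10, either report them with confidence intervals and no significance claim, or adjust them as a family by Holm.

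With one measure, one contrast and one test, the primary error rate is 5%. If the sponsor prefers to keep all variables primary, Bonferroni would need 0.05/6 = 0.0083 each for six variables, or 0.05/11 = 0.0045 for eleven.

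The cost is wording only: no extra subjects, draws or assays. The small downside is that CBC results can no longer be claimed as primary.

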3.4 Secondary Effectiveness Endpoints

Secondary effectiveness endpoints include post-exercise lactate levels, participant demographics, and MSC marker concentrations.

4 Hypotheses

4.1 Null Hypothesis:

H_0 - Subjects will have equal levels of hematopoietic progenitor cells (HPCs) before and after undergoing twelve experimental testing sessions with the Delfi BFR tourniquet system.

4.2 Alternative Hypothesis:

H_1 - Subjects will not have equal levels of hematopoietic progenitor cells (HPCs) before and after undergoing twelve experimental testing sessions with the Delfi BFR tourniquet system.

5 Participant Recruitment and Screening

The research study team intends to enroll a total of 25 volunteers (with 5 expected screen fails or withdraws)

Subject recruitment will occur through the Andrews Institute physician practices and physical therapy departments via word of mouth. Recruitment of subjects will also utilize a flyer displaying the opportunity for subjects to enroll in this study. Flyers will be placed in easily viewed spaces around the Andrews Institute campus in Gulf Breeze, FL. Potential study subjects will undergo a prescreening process covering inclusion and exclusion criteria through standard of care medical evaluations. Potential subjects meeting all inclusion criteria will have the study described to them by a member of the investigating team. This description will include potential risks, discomforts, and benefits. Subjects will then be provided an opportunity to read and sign an approved informed consent form. The subject will be provided sufficient time to consent and sign the informed consent form (ICF). The principal investigator (PI) will be available to answer any questions or provide clarifications during the informed consent process. This process will be completed before conducting any study related activities.

